12.4.6 Supplementary analysis

A supplementary analysis of primary efficacy variable 1 will be based on the following estimand:

- Population: Defined through appropriate inclusion/exclusion criteria to reflect the targeted population
- Variable: Percent change from baseline in LDL-C [The primary analysis time point is at Day 330.]
- Treatment: Inclisiran + usual care or usual care
- Remaining intercurrent events: 1. Potential use of inclisiran by participants in the usual care group. 2. Discontinuation of study treatment. Data after the occurrence of either one of the above two intercurrent events will be excluded from the analysis (using MMRM).
- Summary measure: Least-squares mean difference between inclisiran + usual care group and usual care group

Subgroup analyses of the two primary efficacy variables will be performed by background lipidlowering therapy at baseline. Other subgroups to be considered will be defined in the Statistical Analysis Plan.

12.4.7 Supportive analyses

The primary analysis of the two primary efficacy variables will be repeated for the Per-Protocol Set, Restricted Set 1, and Restricted Set 2.

12.5 Analysis supporting secondary objectives

12.5.1 Efficacy and/or Pharmacodynamic endpoint(s)

The secondary efficacy variables are the following:

- 1. Absolute change from baseline in LDL-C
- 2. Average percent change from baseline in LDL-C levels to each post-baseline visit
- 3. Average absolute change from baseline in LDL-C levels to each post-baseline visit
- 4. Achieving LDL-C < 100 mg/dL (yes, no) (among the subset of participants with LDL- $C \ge 100$ mg/dL at baseline)
- 5. Achieving \geq 50% reduction from baseline in LDL-C (yes, no)
- 6. Achieving LDL-C < 55 mg/dL (yes, no)
- 7. Percent change from baseline in apoB
- 8. Absolute change from baseline in apoB
- 9. Percent change from baseline in VLDL
- 10. Absolute change from baseline in VLDL
- 11. Percent change from baseline in non-HDL-C
- 12. Absolute change from baseline in non-HDL-C
- 13. Percent change from baseline in total cholesterol
- 14. Absolute change from baseline in total cholesterol
- 15. Percent change from baseline in Lp(a)
- 16. Absolute change from baseline in Lp(a)
- 17. Percent change from baseline in HDL-C
- 18. Absolute change from baseline in HDL-C
- 19. Percent change from baseline in triglycerides
- 20. Absolute change from baseline in triglycerides
- 21. Intensity of lipid-lowering therapy (decrease in dose, no change in dose, increase in dose)
- 22. Proportion of days covered (total number of days on either statin, ezetimibe, or PCSK9 inhibiting monoclonal antibody therapies divided by total number of study days)
- 23. Discontinuation of statin therapy (i.e., no statin use \geq 30 days before the end-of-study visit) (yes, no)

Analyses of secondary efficacy variables 1 and 7 - 20 will be similar to the primary analysis of primary efficacy variable 1 (using MMRM, but with a two-sided 95% confidence interval for the treatment difference).

Secondary efficacy variables 2, 3, and 22 will be analyzed using a linear model with treatment and baseline LDL-C as explanatory variables. Least-squares mean of each treatment group, least-squares mean treatment difference, 95% confidence interval for the treatment difference, and p-value based on the fitted model will be reported.

Secondary efficacy variables 4 - 6 and 23 will be analyzed at each post-baseline visit using a logistic regression model with treatment and baseline LDL-C as explanatory variables (Stokes et al 2012). The odds ratio, 95% confidence interval for the odds ratio, and p-value based on the fitted model will be reported. Missing data will be imputed using "non-responder" (i.e., "negative" outcome) imputation.

Secondary efficacy variable 21 will be analyzed at each post-baseline visit using a proportional odds model with treatment and baseline LDL-C as explanatory variables (Stokes et al 2012). The odds ratios, 95% confidence intervals for the odds ratios, and p-values based on the fitted model will be reported. Missing data will not be imputed.

Analyses of secondary efficacy variables will be based on the Full Analysis Set.

12.5.2 Safety endpoints

For all safety analyses, the Safety Set will be used. All listings and tables will be presented by treatment group.

Adverse events

All information obtained on adverse events will be displayed by treatment group and participant.

The number (and percentage) of participants with treatment-emergent adverse events (events started after the first dose of study medication or events present prior to start of double-blind treatment but increased in severity based on preferred term) will be summarized in the following ways:

- by treatment group, primary system organ class and preferred term.
- by treatment group, primary system organ class, preferred term and maximum severity.
- by treatment group, Standardized MedDRA Query (SMQ) and preferred term.

Separate summaries will be provided for study medication related adverse events, death, serious adverse events, other significant adverse events leading to discontinuation.

A participant with multiple adverse events within a primary system organ class is only counted once towards the total of the primary system organ class.

Vital signs

All vital signs data will be listed by treatment group, participant, and visit/time and if ranges are available, abnormalities will be flagged. Summary statistics will be provided by treatment and visit/time.

Clinical laboratory evaluations

All laboratory data will be listed by treatment group, participant, and visit/time, and if reference ranges are available, abnormalities will be flagged. Summary statistics will be provided by treatment and visit/time.

12.5.3 Pharmacokinetics

Not applicable.

12.5.4 DNA

Not applicable.

12.5.5 Biomarkers

See Section 12.5.1.

12.5.6 PK/PD relationships

Not applicable.

[figure not shown]
12.6 Analysis of exploratory endpoints

The exploratory efficacy variables are the following:

- 8. Cardiovascular death (yes, no)
- 9. Non-fatal MI (yes, no)
- 10. Resuscitated cardiac arrest (yes, no)
- 11. Non-fatal ischemic stroke (yes, no)
- 12. Composite MACE (cardiovascular death, non-fatal MI, resuscitated cardiac arrest, or non-fatal ischemic stroke) (yes, no)

12.7 Interim analyses

After all participants complete their baseline visit, the demographic and baseline characteristics may be summarized to help design new studies. No analysis will be performed using post-baseline data. Thus, there is no need to adjust the level of significance for such interim analysis of baseline data.

12.8 Sample size calculation

12.8.1 Primary endpoint(s)

The sample size was calculated for the two primary efficacy variables with adjustment for multiple testing by using the Bonferroni procedure.

For primary efficacy variable 1, i.e., percent change from baseline in LDL-C, the standard deviation is assumed to be 40, partly based on the results from ORION-10 and ORION-11 clinical trials and considering that the standard deviation will likely be larger in this trial since changes in lipid-lowering therapy are allowed in both treatment groups. An expected mean treatment difference of 15 is assumed, which is smaller than the mean difference observed in the Phase III trials, to account for 1) potential lower utilization of background lipid-lowering therapy in the inclisiran + usual care treatment group compared to the usual care treatment group, and 2) the ability to add non-statin lipid lowering therapy, including commercially available inclisiran, in the usual care treatment group. A z-test, an allocation ratio of 1:1, and a two-sided significance level of 0.025 were also used in the calculation of sample size.

Table 12-1 considers total sample sizes for expected mean treatment differences of 10, 15, and 20, and powers of 0.85 and 0.90 (nQuery Version 8.4.1.0). From Table 12-1, an expected mean treatment difference of 15 (based on means of 40 and 55 at Day 330 in the usual care and inclisiran + usual care treatment groups, respectively) and a power of 0.85 were chosen to provide a total sample size of 306 participants.

Table 12-1 Sample size calculations for percent change from baseline in LDL-C

Mean treatment difference	Power = 0.85	Power = 0.90
10	688	796
15	306	354
20	172	200

For primary efficacy variable 2, i.e., achieving LDL-C < 70 mg/dL (yes, no), a z-test, an allocation ratio of 1:1, and a two-sided significance level of 0.025 were used in the calculation of sample size. Table 12-2 considers total sample sizes for several expected proportions of participants who achieve LDL-C < 70 mg/dL at Day 330 in the usual care and inclisiran + usual care treatment groups, and powers of 0.85 and 0.90 (nQuery Version 8.4.1.0). From Table 12-2, the expected proportions of 0.55 and 0.75 in the usual care and inclisiran + usual care treatment groups, respectively, and a power of 0.85 were chosen to provide a total sample size of 242 participants.

Table 12-2 Sample size calculations for achieving LDL-C < 70 mg/dL

Proportion in usual care group	Proportion in inclisiran + usual care group	Power = 0.85	Power = 0.90
0.50	0.65	464	536
0.50	0.70	256	294
0.55	0.70	446	514
0.55	0.75	242	278

Based on the sample size calculations in Table 12-1 and Table 12-2, a total sample size of 306 together with a loss to follow-up rate of 20% at Day 330 require approximately 384 participants (192 participants per treatment group) to be randomized. This will also allow examination of subgroups with reasonable sample sizes.

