The investigator must give the monitor access to all relevant source documents to confirm their consistency with the data capture and/or data entry. Novartis monitoring standards require full verification for the presence of informed consent, adherence to the inclusion/exclusion criteria, documentation of SAEs, and of data that will be used for all primary variables. Additional checks of the consistency of the source data with the CRFs are performed according to the study-specific monitoring plan. No information in source documents about the identity of the participants will be disclosed.

12 Data analysis and statistical methods

Any data analysis carried out independently by the investigator should be submitted to Novartis before publication or presentation.

The analysis will be performed at the end of the trial, after the data for all participants are available.

Unless otherwise specified, all statistical tests will be conducted against a two-sided alternative hypothesis, employing a significance level of 0.05.

Efficacy, safety, and other data will be summarized. For continuous variables, summary statistics (mean, standard deviation, median, 25th and 75th percentiles, interquartile range, minimum, and maximum) at each time point and for change from baseline to each time point will be reported by treatment group. For discrete variables, frequency counts and percentages at each time point will be reported by treatment group.

12.1 **Analysis sets**

The Full Analysis Set (FAS) comprises all randomized participants. According to the intent-totreat principle, participants will be analyzed according to the treatment group they have been assigned to during the randomization procedure.

The Per-Protocol Set is a subset of the Full Analysis Set in which participants are not treated with any inclisiran if they are randomized to the usual care treatment group or do not have any major protocol deviations (including deviations from inclusion/exclusion criteria) in either treatment group.

The Restricted Set 1 is a subset of the Full Analysis Set which includes only participants without changes in background lipid-lowering therapy.

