The primary analysis of primary efficacy variable 2 to address the primary objective will be based on the following estimand:

- Population: Defined through appropriate inclusion/exclusion criteria to reflect the targeted population
- Variable: Achieving LDL-C < 70 mg/dL (yes, no) [The primary analysis time point is at Day 330.]
- Treatment: Inclisiran + usual care or usual care
- Remaining intercurrent events: 1. Potential use of inclisiran by participants in the usual care group. This intercurrent event will be ignored in the analysis, as the design of the trial allows for participants in the usual care group to potentially use inclisiran. 2. Discontinuation of study treatment. This intercurrent event will be ignored in the analysis.
- Summary measure: Odds ratio of inclisiran + usual care to usual care for achieving LDL-C < 70 mg/dL

Let π_j denote the probability of achieving LDL-C < 70 mg/dL at Day 330 for treatment group j, j = 0, 1, where 0 corresponds to usual care and 1 corresponds to inclisiran + usual care. Accordingly, $\pi_i/(1-\pi_i)$ is the odds for treatment group j, j = 0, 1.

The following null hypothesis (H₀) will be tested against the alternative hypotheses (H_A), corresponding to the comparison inclisiran + usual care versus usual care:

$$H_0 \colon [\pi_1/(1-\pi_1)]/[\pi_0/(1-\pi_0)] \leq 1 \text{ versus } H_A \colon [\pi_1/(1-\pi_1)]/[\pi_0/(1-\pi_0)] \geq 1$$

Primary efficacy variable 2 will be analyzed at each post-baseline visit using a logistic regression model with treatment and baseline LDL-C as explanatory variables (Stokes et al 2012). The odds ratio, two-sided 97.5% confidence interval for the odds ratio, and p-value based on the fitted model will be reported. If the p-value based on a two-sided test for inclisiran + usual care versus usual care at Day 330 is < 0.025 and the corresponding odds ratio is greater than 1, statistical significance in favor of inclisiran + usual care is shown.

The primary analysis of both primary efficacy variables will be based on the Full Analysis Set.

Handling of intercurrent events of primary estimand 12.4.3

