12.4.4 Handling of missing values not related to intercurrent event

For the primary analysis of primary efficacy variable 1, the MMRM implicitly imputes missing data under a missing at random assumption.

For the primary analysis of primary efficacy variable 2, participants with missing LDL-C data will be assumed to have LDL-C \geq 70 mg/dL (i.e., "non-responder").

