$$H_0: [\pi_1/(1 - \pi_1)]/[\pi_0/(1 - \pi_0)] \leq 1 \text{ versus } H_A: [\pi_1/(1 - \pi_1)]/[\pi_0/(1 - \pi_0)] > 1$$

Primary efficacy variable 2 will be analyzed at each post-baseline visit using a logistic regression model with treatment and baseline LDL-C as explanatory variables (Stokes et al. 2012). The odds ratio, two-sided 97.5% confidence interval for the odds ratio, and p-value based on the fitted model will be reported. If the p-value based on a two-sided test for inclisiran + usual care versus usual care at Day 330 is < 0.025 and the corresponding odds ratio is greater than 1, statistical significance in favor of inclisiran + usual care is shown. In case of non-

convergence of a logistic regression model, the model will be updated to use Firth's penalized likelihood method (Firth 1993). If the model using Firth's method still shows convergence issues then the baseline LDL-C covariate may be removed from the model. Two-sided 97.5% confidence intervals for the proportion of participants who achieve LDL-C < 70 mg/dL in each treatment group will be calculated, using the normal approximation to the binomial distribution.

The primary analysis of primary efficacy variable 2 will be based on the FAS. The primary analysis of this variable will be repeated for the Per-Protocol Set, Restricted Set 1, and Restricted Set 2.

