- Summary measure: Treatment difference ($[\text{inclisiran + usual care}] - \text{usual care}$) in the proportion of participants who achieve LDL-C < 70 mg/dL

For the above estimand, primary efficacy variable 2 will be analyzed at each post-baseline visit for the FAS using the two-sample z-test (normal approximation to the binomial distribution) to compare inclisiran + usual care versus usual care. Two-sided 97.5% confidence intervals will be calculated, using the normal approximation to the binomial distribution.

For both primary efficacy variables 1 and 2, additional sensitivity analyses will be conducted by repeating the corresponding primary analyses on participants in the Full Analysis Set but excluding participants with baseline LDL-C < 70 mg/dL.

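### Is the second primary variable underpowered because the 20% loss allowance raises N while missing LDL-C is counted as failure?

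*Protocol*

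**What the plan says.** Protocol 12.8.1 and SAP Section 3 give the same calculation. Each primary variable is tested at two-sided 0.025 under a Bonferroni split.

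- **Variable 1** (percent change in LDL-C) needs 306 participants.
- **Variable 2** (LDL-C below 70 mg/dL) is sized by a z-test on "expected proportions of 0.55 and 0.75 in the usual care and inclisiran + usual care treatment groups, respectively, and a power of 0.85", which gives 242.
- **Loss:** the larger number is carried forward, so that "a total sample size of 306 together with a loss to follow-up rate of 20% at Day 330 require approximately 384 participants". The loss rate is used nowhere else.

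The analysis of variable 2 is set out separately. In Protocol 12.1, "The Full Analysis Set (FAS) comprises all randomized participants". In Protocol 12.4.2, "The primary analysis of both primary efficacy variables will be based on the Full Analysis Set", and SAP 2.5.2 agrees: "The primary analysis of primary efficacy variable 2 will be based on the FAS". The primary test comes from a "logistic regression model with treatment and baseline LDL-C as explanatory variables". Under Protocol 12.4.4 and SAP 2.5.4, "participants with missing LDL-C data will be assumed to have LDL-C" of at least 70 mg/dL, which makes them non-responders. The unadjusted z-test on the full analysis set is a sensitivity analysis (SAP 2.5.5). An analysis restricted to observed values is supplementary (SAP 2.5.6).

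**The concern.** Dividing a sample size by one minus the loss rate suits an analysis that loses those participants. It restores the number analysed and leaves the treatment difference alone. Variable 2 is not analysed that way. A participant with no Day 330 value stays in the denominator as a failure, so equal loss in both arms multiplies both response rates by the same factor and shrinks their difference. Raising N from 306 to 384 does not correct for that.

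The documents do not say whether 0.55 and 0.75 are rates among participants with a value or rates after missing values are scored as failures. They also give no power for variable 2 at 384. If the rates are of the first kind, one of the two primary variables could have less than the 0.85 power used to size it. A non-significant result on it would then be harder to interpret.

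**Working it through.** **Inputs.** From Protocol 12.8.1: two-sided alpha 0.025 (critical value 2.2414), power 0.85 (normal quantile 1.0364), rates 0.55 and 0.75, 1:1 allocation, 20% loss, 192 per arm.

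**Reproducing the plan.** The pooled z-test sample size per arm is

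n = [2.2414·√(2p̄(1−p̄)) + 1.0364·√(p₀(1−p₀)+p₁(1−p₁))]² / (p₁−p₀)²

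With p₀ = 0.55, p₁ = 0.75 and p̄ = 0.65, the two square roots are 0.6745 and 0.6595. This gives n = 120.5, so 121 per arm and 242 in total, as stated. For variable 1, 2·(2.2414+1.0364)²·40²/15² = 152.8, so 153 per arm and 306 in total. Then 306/0.8 = 382.5, and 192 per arm makes 384. All three figures are right.

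**Power at 192 per arm.** The same formula turned round is

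power = Φ{[(p₁−p₀)·√192 − 2.2414·√(2p̄(1−p̄))] / √(p₀(1−p₀)+p₁(1−p₁))}

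- *Rates already count missing as failure* (0.55 and 0.75): Φ(1.909) = 0.972. With 20% loss, the implied rates among participants with a value are 0.55/0.8 = 0.6875 and 0.75/0.8 = 0.9375.
- *Rates are before the rule, 20% missing in each arm*: 0.55·0.8 = 0.44 and 0.75·0.8 = 0.60, so the difference falls from 0.20 to 0.16. With p̄ = 0.52 the square roots are 0.7065 and 0.6974, and power is Φ(0.908) = 0.818 (0.826 with unpooled variance). Reaching 0.85 would take 416 randomized.

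Power on the second reading, by equal loss in each arm:

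| Loss | Analysed rates | Power |
|---|---|---|
| 10% | 0.495, 0.675 | 0.913 |
| 15% | 0.4675, 0.6375 | 0.870 |
| 17% | 0.4565, 0.6225 | 0.850 |
| 20% | 0.44, 0.60 | 0.818 |
| 25% | 0.4125, 0.5625 | 0.760 |

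**The planned test.** The primary test is the logistic model with baseline LDL-C, not the z-test. The documents give no strength for the baseline effect, so a range is assumed. Simulation (20,000 runs, 192 per arm, marginal rates held at 0.55 and 0.75, 20% loss unrelated to baseline or outcome) gives power of 0.824, 0.828 and 0.857 for baseline effects of 0, 0.5 and 1 log-odds per standard deviation. Zero is the pessimistic end: for a given percent reduction, a participant who starts higher is less likely to get below 70 mg/dL.

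**Scale.** In the plan's own table, lowering the inclisiran rate from 0.75 to 0.70 against 0.55 raises the required total from 242 to 446. With 192 per arm and complete data, that change takes power from 0.972 to Φ(0.804) = 0.789. The choice of rates therefore matters more than the 3-point gap between 0.85 and 0.82.

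**The case for a change.** The strongest case for a change is that variable 2 is a primary variable with its own 0.025, and that its power under its own missing-data rule cannot be read from either document. Twenty percent is the sponsor's own planning figure, so it is fair to carry it through. The before-rule reading also has support. Loss is allowed for as a separate step, and the other reading implies that about 94% of inclisiran participants with a value are below 70 mg/dL, whereas Protocol 1.1.5 reports more than 65% in the Phase III trials. Two or three sentences would settle the matter.

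The silence is real, and that part stands. The rest is weaker.

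- **The text does not settle the reading.** Section 12.8.1 speaks of the proportion achieving the target in each treatment group, which is also how the full-analysis-set comparison is described. Where the SAP means observed values only, in 2.5.6, it says so and changes the denominator. The Phase III population had stable disease, so its rate is only indirect evidence.
- **The 0.82 needs the whole 20% to lack a Day 330 value, equally by arm.** Follow-up continues after treatment stops, home blood draws are allowed, and SAP 2.1.1 accepts scheduled or unscheduled values from study days 301 to 375. Power is also sensitive to the split. On the before-rule reading, 15% loss in usual care and 25% in the inclisiran arm gives 0.35, and the reverse gives 0.99. A sentence quoting one power for equal loss would be more precise than its inputs. What uneven loss does to the comparison is a separate matter, and the observed-value analysis in SAP 2.5.6 bears on it.
- **The cost is more than a few sentences.** Protocol 14.1 requires a written, approved amendment for any protocol change, which is out of proportion for restating planning power.

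**Conclusion.** No change follows. The sample size is set by variable 1, each stated number is correct for what it claims, and neither document claims 0.85 for variable 2 at 384. Power for variable 2 at that size is about 0.97 if the planning rates already score missing values as failures. If they do not, and 20% of each arm has no Day 330 value, it is about 0.82 for the sizing z-test and 0.82 to 0.86 for the planned logistic test, depending on an assumed baseline effect. On the less favourable reading the planned test therefore lies between about 3 points below the 0.85 used for sizing and slightly above it. At 17% loss or less even the z-test reaches 0.85.

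Stating which reading was meant would document an assumption without altering the sample size, the model, the missing-data rule, the decision rule or any conclusion. A note in SAP Section 3 would be harmless if that document were reissued for another reason, but nothing in the trial depends on it.
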